6.7. Concomitant Therapy

Any medication or vaccine (including over-the-counter or prescription medicines, vitamins, and/or herbal supplements) that the participant is receiving at the time of enrollment or receives during the study must be recorded along with:

- reason for use
- dates of administration including start and end dates
- dosage information including dose and frequency

Concomitant medications (prescription and non-prescription) should be administered only as medically necessary during the study. All concomitant medications, blood products, and vaccines (clinicians should work with participants regarding the timing of licensed vaccines relative to study product administration) taken during the study will be recorded in the eCRF with dates of administration.

Non-protocol defined treatments or medical interventions (e.g., physical therapy, radiotherapy, surgical procedures) are permitted during the study for appropriate medical management of the participant.

The Medical Monitor should be contacted if there are any questions regarding concomitant or prior therapy.

7. DISCONTINUATION OF STUDY INTERVENTION AND PARTICIPANT DISCONTINUATION/WITHDRAWAL

7.1. Discontinuation of Study Intervention

Emerging safety data will be reviewed in-stream as the study progresses and the following criteria will result in a study pause. A full safety review will be conducted, and the findings and recommendations presented to ViiV Safety and Labelling Committee (VSLC) for endorsement:

- Any SAE, regardless of its severity, that is considered be clinically significant and reasonably attributable to dosing with GSK3810109, in the opinion of the investigator and sponsor.
- Acute allergic reaction or CRS (Division of AIDS [DAIDS] criteria Grade 3 to 4) reasonably attributable to dosing with GSK3810109, in the opinion of the investigator and sponsor.
- Any AE of Grade 4 intensity assessed as related to GSK3810109, as reported by the investigator.
- Any participant meeting liver chemistry stopping criteria (see Section [7.2](#))
- Any participant meeting QTcF stopping criteria (see Section [7.3](#))
- If 2 participants in any discrete part of the study (Part 1, Part 2, or Part 3) experience an AE of Grade 3 intensity (excluding ISRs) assessed as related by the investigator.
- If 2 or more injections/infusions administered in any discrete part of the study (Part 1, Part 2, or Part 3) are followed by an ISR of at least Grade 3 in severity.

Note: Grade 3 ISRs that are based on the size of erythema or induration alone will not be considered as a pausing criterion. However, any Grade 3 ISR of erythema or induration due to ulceration, secondary infection, phlebitis, sterile abscess, drainage, or symptoms causing inability to perform usual social and functional activities (as per DAIDS) will be included as a pausing criterion.

Relevant reporting and discussion with the Medical Monitor, relevant study team personnel, and the institutional review board (IRB)/independent ethics committee (IEC) will take place before resumption of dosing. Every effort will be made to take a blood sample at the time of the AE for PK analysis.

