6.1. Study Interventions Administered

Table 1 Study Interventions Administered

| Intervention Label | | |
|--------------------------|------------------------------------------------------------------------------------------------------------------------------------------------------------------------------------------------------|---------------------------------------------------------------------------------------------------------------------------------------------------------------------------------------------------------------------------------------------------------------------------------------------------------------------------------------|
| Intervention on Label | GSK3810109 | rHuPH20 |
| Intervention Description | GSK3810109 is a clear, colorless to yellow liquid that is essentially free of visible particles; the product is supplied as a sterile aqueous buffered solution filled into 10 mL single-dose vials. | Each vial of ENHANZE™ Drug Product (EDP) contains 0.5 mL of rHuPH20 formulated at a concentration of 1 mg/mL (~110,000 U/mL rHuPH20). EDP is manufactured by Ajinomoto Althea, Inc, (San Diego, CA) for Halozyme Therapeutics, Inc. (San Diego, CA) and is supplied in 2 mL glass vials as a sterile, single-dose, injectable liquid. |
| Type | Biologic | Biologic |
| Dose Formulation | Vial | Vial |
| Unit Dose Strength | 600 mg/6mL vial | Each vial of EDP contains 0.5 mL of rHuPH20 formulated at a concentration of 1 mg/mL (~110,000 U/mL rHuPH20) |
| Dosage Level | For Part 1, SC infusion 20 mg/kg For Part 2, IV infusion 60 mg/kg CCI [REDACTED] | 2000 U/mL based on dose of GSK3810109 |
| Route of Administration | SC infusion/IV infusion | SC infusion |
| Use | Experimental | Experimental |
| IMP and NIMP | IMP | IMP |

| | | |
|-------------------------------------|--------------------------------------------------------------------------------------------------------------|--------------------------------------------------------------------------------------------------------------|
| Intervention Label | | |
| Sourcing | Provided by the sponsor | Provided by the sponsor |
| Packaging and Labeling | Study intervention will be provided in vials. Each vial will be labeled as required per country requirement. | Study intervention will be provided in vials. Each vial will be labeled as required per country requirement. |
| Current/Former Name or Alias | GSK3810109 /VH3810109/ N6LS | Enhance TM Drug Product (EDP) |

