6.2. Study Product Administration

Subcutaneous Administration with rHuPH20

The SC administration site(s) to be used must be assessed as acceptable by the clinician and the participant. The preferred SC administration site is the abdomen. GSK3810109 will be mixed with rHuPH20 in the pharmacy and then administered via standard Medfusion 3500 syringe pump (or equivalent) in 1 infusion site at a rate of no more than 3 mL/minute. For Part 1, given the weight criterion in this study, the maximum volume needed to administer a 20 mg/kg SC dose is not expected to exceed 24 mL. **CCI** [REDACTED]

[REDACTED]. If the participant experiences side effects during the infusion, the rate of infusion may be slowed or stopped to alleviate the symptoms.

Intravenous Administration

For Part 2, participants will receive IV administration of GSK3810109. The IV access will be placed in an arm vein in an aseptic manner. A different site should be used for collection of PK blood samples; however, the same site may be used after flushing the line if another site is not available. GSK3810109 will be diluted with normal saline to infuse approximately 250 mL of solution at the appropriate concentration (as described in the current IB [[Investigator's Brochure](#)]) over about 60 minutes. The entire infusion should not exceed 2 hours. If the participant experiences side effects during the infusion, the rate of infusion may be slowed or interrupted to alleviate the symptoms.

There are no pre-medications for IV administration; however, based on emerging safety data from sentinel participants, these may be given at the investigator's discretion and in consultation with the Medical Monitor.

Study Product and Administration Regimen

GSK3810109 is a clear, colorless to yellow liquid, that is essentially free of visible particles; the product is supplied as a sterile aqueous buffered solution filled into 10 mL single-dose vials. Each vial contains a 6.25 ± 0.10 mL volume of GSK3810109 at a concentration of 100 ± 10 mg/mL in a formulation buffer composed of 10 mM sodium citrate, 50 mM sodium chloride, 150 mM arginine-hydrochloride, and 0.002%

polysorbate-80 at pH 6.5. Vials have a nominal fill volume of 6.25 mL to enable withdrawal up to 6.0 mL.

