6.6. Overdose

For this study, any administered dose of GSK3810109 and/or rHuPH20, greater than that intended for the study will be considered an overdose.

The investigator should use clinical judgment in treating overdose, as ViiV Healthcare is unable to recommend specific treatment other than supportive care.

In the event of an overdose, the investigator/treating physician should:

1. Contact the Medical Monitor immediately.
2. Monitor vital signs regularly for several hours after the overdose.
3. Closely monitor the participant for AE/SAE and laboratory abnormalities until GSK3810109 can no longer be detected systemically.
4. Obtain a sample for PK analysis from the date of the overdose of study intervention if requested by the Medical Monitor (determined on a case-by-case basis).
5. Document the quantity of the excess dose as well as the duration of the overdosing in the eCRF.

Since this is a single-dose administration of GSK3810109, dose modifications will not be applicable. However, if the participant experiences side effects during the infusion, the rate of infusion may be slowed or stopped to alleviate the symptoms.

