| 
The investigator will make an assessment of intensity for each AE and SAE reported during the study and assign it to one of the following categories:
 
 Mild: Asymptomatic or mild symptoms; clinical or diagnostic observations only; intervention not indicated. Moderate: Minimal, local or non-invasive intervention indicated; limiting age-appropriate instrumental Activities of Daily Living (ADL). Instrumental ADL refers to preparing meals, shopping for groceries or clothes, using the telephone, managing money, etc. Severe: Severe or medically significant but not immediately life-threatening; hospitalization or prolongation of hospitalization indicated; disabling, limiting self-care ADL. Self-care ADL refers to bathing, dressing and undressing, feeding self, using the toilet, taking medications, and not bedridden. |

Assessment of Causality

- The investigator is obligated to assess the relationship between study intervention and each occurrence of each AE/SAE. The investigator will use clinical judgment to determine the relationship.
- *A reasonable possibility* of a relationship conveys that there are facts, evidence, and/or arguments to suggest a causal relationship, rather than a relationship cannot be ruled out.
- Alternative causes, such as underlying disease(s), concomitant therapy, and other risk factors, as well as the temporal relationship of the event to study intervention administration will be considered and investigated.
- The investigator will also consult the IB and/or Product Information, for marketed products, in his/her assessment.
- For each AE/SAE, the investigator **must** document in the medical notes that he/she has reviewed the AE/SAE and has provided an assessment of causality.
- There may be situations in which an SAE has occurred, and the investigator has minimal information to include in the initial report to ViiV/GSK. However, **it is very important that the investigator always make an assessment of causality for every event before the initial transmission of the SAE data to ViiV/GSK.**
- The investigator may change his/her opinion of causality in light of follow-up information and send an SAE follow-up report with the updated causality assessment.
- The causality assessment is one of the criteria used when determining regulatory reporting requirements.

Follow-up of AE and SAE

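### In the SC parts, the Grade 4 pause criterion names only GSK3810109, so read literally one Grade 4 event attributed to rHuPH20 alone would not force a pause under it

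*Protocol*

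**What the plan says.** Section 7.1 of the protocol lists the events that oblige the sponsor to pause the study. Three of the seven criteria name the antibody in their attribution test:

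- Grade 4 AE: "Any AE of Grade 4 intensity assessed as related to GSK3810109, as reported by the investigator".
- SAE: "Any SAE, regardless of its severity, that is considered be clinically significant and reasonably attributable to dosing with GSK3810109", in the joint opinion of investigator and sponsor.
- Allergic reaction or cytokine release syndrome (CRS): "Acute allergic reaction or CRS (Division of AIDS [DAIDS] criteria Grade 3 to 4) reasonably attributable to dosing with GSK3810109", again in the joint opinion of investigator and sponsor.

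The Grade 3 criterion asks only that the investigator consider the event related and names no product. The injection site reaction (ISR) criterion begins "If 2 or more injections/infusions administered in any discrete part of the study" and has no attribution test. The liver and QTcF criteria have none either.

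Elsewhere the protocol treats the subcutaneous dose as two products. Table 1 in section 6.1 classes both the same way ("IMP and NIMP | IMP | IMP"). Section 6.2 states that "GSK3810109 will be mixed with rHuPH20 in the pharmacy". Section 6.6 names both: "any administered dose of GSK3810109 and/or rHuPH20, greater than that intended for the study will be considered an overdose". On causality, section 10.3.3 says: "The investigator is obligated to assess the relationship between study intervention and each occurrence of each AE/SAE".

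**The concern.** A mandatory pause rule should cover everything that is injected. In Parts 1 and 3 the participant receives antibody and enzyme together, yet the Grade 4 criterion tests relatedness to the antibody only. It is also out of step with the criterion one grade lower: two related Grade 3 events in a part (other than ISRs) force a pause whichever product is blamed, while one Grade 4 event blamed on the enzyme does not. The more severe grade has the narrower attribution test, and nothing visible in the protocol explains why.

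If such an event occurred and no other criterion caught it, a pause would rest on a recommendation from the Safety Review Team (SRT) and a decision by the sponsor's safety committee (section 10.1.5). Scheduled review is lighter in these parts than in Part 2. Part 1 describes no sentinel participants and relies on monthly SRT meetings. Part 3 describes a core SRT review after the first 2 participants, and the readable text gives no review step among the next 6.

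**Working it through.** The plan states no figure for this rule, so the check is textual. Take one Grade 4 AE in Part 1 or Part 3, attributed to rHuPH20 alone, and run it through section 7.1 under two readings of the phrase on dosing with GSK3810109: the mixed dose, or the antibody only.

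| Criterion | Events needed | Product named | Pause if phrase means mixed dose | Pause if phrase means antibody only |
|---|---|---|---|---|
| SAE | 1 | GSK3810109 (dosing with) | If serious and judged clinically significant and attributable | No |
| Allergic reaction/CRS, Grade 3 to 4 | 1 | GSK3810109 (dosing with) | If it is such a reaction | No |
| Grade 4 AE | 1 | GSK3810109 (related to) | No | No |
| Liver | 1 | None | If ALT is at least 3 × ULN | Same |
| QTcF | 1 | None | If QTcF > 480 msec or change > 60 msec | Same |
| Grade 3 AE | 2 participants | None | No | No |
| ISR, Grade 3 or higher | 2 administrations | None | No | No |

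I read the note under the ISR criterion as saying which Grade 3 reactions count toward the two, not as a separate single-event trigger.

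**Counts.**
- Single-event criteria: 5. Two-event criteria: 2. Total: 5 + 2 = 7.
- Mixed-dose reading: 1 of 7 limited. Single-event backstops left: 5 − 1 = 4 (SAE, allergic reaction/CRS, liver, QTcF).
- Antibody-only reading: 1 + 2 = 3 of 7 limited. Single-event backstops left: 5 − 3 = 2 (liver, QTcF).
- Unaffected under either reading: 7 − 3 = 4.

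**Does the SAE criterion already cover Grade 4 events?** Largely, on the mixed-dose reading. The functional Grade 4 definition in Appendix 7 describes potentially life-threatening symptoms that call for intervention to avert lasting harm or death. The life-threatening limb of the SAE definition (10.3.2 b) is narrower, because it leaves out events that would have threatened life only had they been worse. Limb (f) closes most of that difference: it takes in events that may endanger the participant or need intervention to prevent a serious outcome, and says these should usually be considered serious. Two differences remain. Laboratory abnormalities are also graded (section 8.2), and a Grade 4 value need not be an SAE. The SAE criterion also adds a clinical-significance test and the sponsor's opinion, while the Grade 4 criterion needs only the investigator's report.

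**Enzyme dose in Part 1.** 20 mg/kg ÷ 100 mg/mL = 0.2 mL/kg; × 2000 U/mL = 400 U/kg. At 70 kg this gives 400 × 70 = 28,000 U, as section 4.1 states. Section 4.2 cites undetectable systemic exposure up to 30,000 U SC, which is reached at 30,000 ÷ 400 = 75 kg. The weight limits of 50 to below 100 kg give 20,000 to below 40,000 U, inside the 15 to 96,000 U used in other studies (section 2.2.2). The Part 3 dose is redacted and cannot be computed. Part 2 contains no rHuPH20.

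**The case against.** The best defence is that the drug code is shorthand for the whole injection. Section 3 counts ISRs from GSK3810109 administration and section 8.2.7.1 speaks of the GSK3810109 injection, both meaning the mixed dose. On that view the unnamed product in the Grade 3 criterion shows loose drafting rather than an intended restriction, and no criterion is limited. This is plausible, and site staff may well read it that way. It is weaker for the Grade 4 criterion than for the other two. The uses in sections 3 and 8.2.7.1 fix timing, whereas relatedness to GSK3810109 is a causal judgement about a named product.

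The second defence is that the scenario needs a judgement nobody is asked to make. Section 10.3.3 asks for causality to study intervention, SAP 4.2.2 refers to one treatment relationship, and the two products enter through one infusion site. This stands: enzyme-only attribution would be unusual.

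Third, the rHuPH20 risks in section 2.3.1 are spread of infection, hypersensitivity, inadvertent IV administration, mostly mild ISRs, and headache. No laboratory toxicity is listed, which is where the Grade 4 and SAE definitions differ most. Serious or Grade 3 and higher ISRs go to the Medical Monitor, safety concerns go to the sponsor at once, SAEs are reported within 24 hours, and data are reviewed in-stream. All of this stands and limits the practical weight of the point. None of it puts the enzyme inside the mandatory Grade 4 rule.

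A reader might infer that the sponsor meant to exempt the enzyme, or that dosing would continue unexamined after such an event. The documents support neither. The wording elsewhere suggests an oversight, and the SRT can recommend a pause for any safety finding.

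**Conclusion.** The point holds as a minor weakness in a mandatory safety rule for Parts 1 and 3. On its wording, the Grade 4 criterion does not reach a single event attributed to rHuPH20 alone. Its extent depends on reading: 1 of 7 criteria limited with four single-event backstops, or 3 of 7 limited with two. The text does not settle which, so neither count should be presented as definite.

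The conclusion assumes that the Grade 4 wording is applied literally, that an investigator separates the enzyme from the antibody, and that no redacted Part 3 text adds a rule. Section 7.1 as printed does cover Part 3.

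A reader might want a probability of a missed pause. None can be given: the documents state no rate of enzyme-only Grade 4 events, and any figure would only restate an assumed rate. Nor does the dose arithmetic show an untested exposure; it shows only that some Part 1 participants would exceed the dose up to which exposure is described as undetectable.

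**What to change.** Edit three criteria in section 7.1:

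- Grade 4 AE: *related to study intervention (GSK3810109 and/or rHuPH20)*.
- SAE and allergic reaction/CRS: *dosing with study intervention (GSK3810109 and/or rHuPH20)*. This settles the reading of both.

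Leave the grades, event counts and other four criteria unchanged. The wording also works for Part 2, where only GSK3810109 is given. No SAP change is needed. The cost is one phrase in each of three criteria and, at most, an occasional extra safety review for an event due to the enzyme alone.

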In Part 1, approximately 8 participants will receive a single 20 mg/kg SC dose of GSK3810109 co-administered with rHuPH20 at a dose of 2000 U/mL or ~28,000 U for a 70 kg participant. The participants will be admitted in the clinic on Day -1 and the study product will be administered on Day 1. The participants will remain in the clinic for approximately 8 hours for study-related procedures after study product administration and will be followed up for 24 weeks.

Safety laboratory samples will be collected throughout the study as per the Schedule of Activities (SoA). The primary endpoint of injection site reaction (ISR) will be evaluated at specified time points up to Day 7; study participants will keep a diary of ISRs for 14 days after study product administration. Symptoms, maximum intensities, and durations will be reported through end of study to characterize presentation and resolution of local ISRs.

In Part 2, approximately 8 participants will receive a single 60 mg/kg IV dose of GSK3810109. A sentinel cohort of 2 participants will be used to mitigate the risk of unexpected AEs prior to dosing of the remaining 6 participants, who will be dosed in sequential cohorts of 2 participants each.

The sentinel cohort of 2 participants will be admitted to the clinic on Day –1. The study product will be administered on Day 1 and participants will remain in the clinic and be monitored for 7 days after study product administration. The participants will be discharged from the clinic on Day 8 and will be followed up for 24 weeks.

Following Day 10 visit, core Safety Review Team (SRT) will review the safety data (safety laboratory data, electrocardiogram, and AEs) from the sentinel cohort and may

recommend continuation of the study where the next cohort of 2 participants will be dosed.

The second cohort of 2 participants will be admitted to the clinic on Day –1. The study product will be administered on Day 1 and participants will remain in the clinic and be monitored for 7 days after study product administration. The participants will be discharged from the clinic on Day 8 and will be followed up for 24 weeks. A review of at least AE data from this cohort will be conducted after a minimum of 4 days following infusion of GSK3810109 and the core SRT may recommend continuation of the study where the next cohort of 2 participants will be dosed.

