8.2.1. Time Period and Frequency for Collecting AE and SAE Information

- All SAEs will be collected from the start of study intervention until the last visit at the time points specified in the SoA (Section 1.5, Section 1.6, and Section 1.7). However, any SAEs assessed as related to study participation (e.g., study intervention, protocol-mandated procedures, invasive tests, or change in existing therapy) or related to a ViiV/GSK product will be recorded from the time a participant consents to take part in the study.
- All AEs will be collected from the start of intervention until last study visit at the time points specified in the SoA (Section 1.5, Section 1.6, and Section 1.7).
- Medical occurrences that begin before the start of study intervention but after obtaining informed consent will be recorded in the Medical History/Current Medical Conditions section of the eCRF not the AE section.
- All SAEs will be recorded and reported to the sponsor or designee immediately and under no circumstance should this exceed 24 hours, as indicated in Section 10.3.4. The investigator will submit any updated SAE data to the sponsor within 24 hours of it being available.
- Investigators are not obligated to actively seek AEs or SAEs after the conclusion of the study participation. However, if the investigator learns of any SAE, including a death, at any time after a participant has been discharged from the study, and he/she considers the event to be reasonably related to the study intervention or study participation, the investigator must promptly notify the sponsor.

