10.3.2. Definition of SAE

| | |
|---------------------------------------------------------------------------------------------------------------------------------|---------------------------------------------------------------------------------------------------------------------------------------------------------------------------------------------------------------------------------------------------------------------------------------------------------------------------------------------------------------------------------------------------------------------------------------------------------------------------------------------------------------------------------------------------------------------------------------------------------------------------------------------------------------------------------------------------------------------------------------------------------------------------------------------------------------------------|
| 
An SAE is defined as any untoward medical occurrence that, at any dose, meets one or more of the criteria listed:
 | |
| a. Results in death | |
| b. Is life-threatening | 
The term 'life-threatening' in the definition of 'serious' refers to an event in which the participant was at risk of death at the time of the event. It does not refer to an event, which hypothetically might have caused death, if it were more severe.
 |
| c. Requires inpatient hospitalization or prolongation of existing hospitalization | 
 • In general, hospitalization signifies that the participant has been admitted (usually involving at least an overnight stay) at the hospital or emergency ward for observation and/or treatment that would not have been appropriate in the physician's office or outpatient setting. Complications that occur during hospitalization are AE. If a complication prolongs hospitalization or fulfills any other serious criteria, the event is serious. When in doubt as to whether "hospitalization" occurred or was necessary, the AE should be considered serious. • Hospitalization for elective treatment of a pre-existing condition that did not worsen from baseline is not considered an AE. |

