- For severity grading of the solicited bruising parameter at the product administration site, the definitions based on size of the largest diameter and listed for the "Injection Site Erythema or Redness" will be used. The severity grade definition for "Bruising" provided under the Dermatologic Clinical Conditions will be used only for unsolicited adverse events involving bruising at other body locations.
- Creatinine changes will be graded on the basis of the upper limit of normal provided by the grading table and not change from baseline.
- Creatinine clearance changes will be graded according to mL/minute provided by the grading table and not change from baseline.
- Subclinical comprehensive metabolic panel results for sodium, potassium, chloride, bicarbonate, BUN, and glucose will not be considered an AE unless Grade 2 or greater.

[figure not shown]
Estimating Severity Grade for Parameters Not Identified in the Grading Table

The functional table below should be used to grade the severity of an AE that is not specifically identified in the grading table. In addition, all deaths related to an AE are to be classified as **Grade 5**.

| Parameter | Grade 1 Mild | Grade 2 Moderate | Grade 3 Severe | Grade 4 Potentially Life-Threatening |
|----------------------------------------------------------------------|----------------------------------------------------------------------------------------------------------------------------|-----------------------------------------------------------------------------------------------------------------------------------|----------------------------------------------------------------------------------------------------------------------------------|-------------------------------------------------------------------------------------------------------------------------------------------------------------------------------------------|

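### The pause rule that rests on the investigator's judgement alone stops at Grade 4, so a related event first graded 5 (fatal) faces a stricter pause test than a related Grade 4 event

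*Protocol*

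**What the plan says.** Protocol Section 7.1 lists the events that pause the study. Three bullets matter here.

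- **SAE bullet.** It covers "Any SAE, regardless of its severity, that is considered be clinically significant". A second condition concerns causality: the event has to be "reasonably attributable to dosing with GSK3810109, in the opinion of the investigator and sponsor". Both parties must hold that view.
- **Single-event AE bullet.** It covers "Any AE of Grade 4 intensity assessed as related to GSK3810109, as reported by the investigator". The sponsor's opinion is not required.
- **Injection site reaction bullet.** It applies when two or more administrations in a study part "are followed by an ISR of at least Grade 3 in severity". This threshold is open at the top.

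On grading, Section 8.2 assigns AE intensity by the DAIDS table. Appendix 7 (Section 10.7) adds: "In addition, all deaths related to an AE are to be classified as" Grade 5. The functional grading table in that appendix has four columns and ends at Grade 4, potentially life-threatening. In Section 10.3.2 the leading SAE criterion is "Results in death".

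On other safeguards, Section 8.2.1 states: "All SAEs will be recorded and reported to the sponsor or designee immediately and under no circumstance should this exceed 24 hours". After each of the early cohorts in Part 2, the Synopsis says that "the core SRT may recommend continuation of the study where the next cohort of 2 participants will be dosed" or gives equivalent wording. Section 10.1.5 has the core Safety Review Team (SRT) review the first two Part 3 participants before the other six are enrolled.

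**The concern.** Pause criteria should become no harder to meet as the outcome worsens. Here the route that depends only on the investigator's causality judgement is available at Grade 4 and, read literally, closed at Grade 5. A fatal event has to go through the SAE bullet, where the sponsor's agreement on attribution is a condition.

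These rules protect participants who have not yet been dosed. The point deserves attention in this study for two reasons. No data and safety monitoring board is empaneled, and final decisions on modification or termination rest with a committee chaired by the sponsor's chief medical officer (Synopsis). Also, Part 2 gives healthy adults 60 mg/kg IV, when no single human dose had exceeded 40 mg/kg. The investigator-only bullet is the one single-event AE trigger that does not depend on the sponsor's view of causality.

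**Working it through.** The check is mainly a reading of the triggers, since the plan gives no figure to reproduce. Take one event that the investigator calls related and that meets no liver, QTcF or injection site reaction criterion, and apply Section 7.1 literally.

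| Event | Sponsor agrees on attribution? | SAE bullet | Single-event AE bullet | Pause? |
|---|---|---|---|---|
| Grade 4 | No | Not met | Met | Yes |
| Grade 5 (death) | Yes | Met | Not met | Yes |
| Grade 5 (death) | No | Not met | Not met | **No** |

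The first and third rows differ only in grade, and the worse grade has the weaker protection.

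The other bullets do not close the gap:

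- The two-participant bullet is also investigator-assessed, but it names Grade 3 and needs two participants, so one death cannot meet it.
- The allergic reaction and cytokine release bullet stops at Grade 4 and needs the sponsor's opinion in any case.

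The gap is confined to an event whose first reported grade is 5. One reported earlier as related Grade 4 would already have paused the study.

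**Prior experience** (Protocol Section 4.3): 38 HIV-uninfected + 14 HIV-infected adults = 52 dosed, with no SAEs or deaths reported. Complete safety information was available for 36. None had received a single dose above 40 mg/kg.

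**Participants who could still be dosed in a part without a new core SRT recommendation:**

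- Part 2 (pairs): 2 − 1 = 1 if the event falls within a pair; 2 if the next pair has already been cleared. The second case is possible because the reviews after the second and third cohorts need at least AE data after a minimum of 4 days, while follow-up runs to 24 weeks.
- Part 3 (2, then 6): 6 − 1 = 5 if the event falls within the second cohort; 6 if that cohort has been cleared but not yet dosed.
- Part 1: no figure. SAP Section 1.2 describes the parts as sequential, and the documents do not show Part 1 dosing still open.

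These are upper limits. They assume that participants within a cohort are not dosed at the same moment. Part of the Part 3 description is redacted, so any further staggering within its cohorts cannot be seen.

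**The case against.** The strongest reply is that this is a drafting convention and not a gap. Two other bullets also use closed grades (Grade 3 to 4 for allergic reactions, Grade 3 for the two-participant rule), and the functional table ends at Grade 4. The authors may have treated 4 as the ceiling and death as an outcome, not an intensity. No sensible investigator or medical monitor would continue dosing after a related death because the bullet says 4.

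The SAE bullet also covers a related death already, so what remains needs a sponsor to reject attribution of a death that the investigator calls related. Other routes exist: in-stream safety review, 24-hour SAE reporting, immediate discussion of safety concerns with the sponsor (Section 8), urgent changes to remove an immediate hazard (Section 10.1.1), and site closure by the investigator (Section 10.1.9). The investigator's report in any case only starts a pause; the review findings go to the sponsor's safety committee for endorsement.

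Most of this stands as an argument about likelihood. It does not settle the wording. The convention is nowhere stated, the same list uses an open-ended threshold for injection site reactions, and SAP Section 4.2.2 tabulates injection site reaction AEs by maximum grade up to 5, so Grade 5 is in use as a category. The alternative routes either run through the sponsor or are not automatic pauses, so they do not restore what the bullet provides at Grade 4.

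**Conclusion.** The point holds as a minor defect in a decision rule: followed exactly as written, one threshold is out of order at its top grade. It is worth considering, not a major finding.

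The likelihood is very low, because four things must coincide: a death that the investigator calls related, no earlier related Grade 4 report of the same event, no liver, QTcF or injection site reaction trigger met, and a sponsor that does not agree on attribution. Even then, the number exposed without a new core SRT recommendation is bounded as shown above, and the site, the medical monitor and the ethics committee would all have reason to intervene. No endpoint, estimand or analysis changes.

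The conclusion rests on a literal reading of the bullet. If the authors meant Grade 4 to include anything worse, the intent is sound and only the text needs to say so.

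**What to change.** In the single-event AE bullet of Section 7.1, replace *Grade 4* with *Grade 4 or higher (including Grade 5)* and keep the rest, so that relatedness remains as reported by the investigator. Leave the SAE bullet and the allergic reaction and cytokine release bullet as they are; once this bullet is open at the top, a related death pauses the study whether or not the sponsor agrees on attribution.

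The change is a few words at the next amendment, with no extra data, visits or staff. Its only downside is a possible additional pause and safety review after a death that the investigator considers related.
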